### **6.2.2 Nivolumab**

Nivolumab will be supplied by 240 mg/24 mL vial solutions for infusion after dilution. Two (2) vials will be needed for the 480 mg dose.

Storage;

- Unopened vials must be stored in a refrigerator (2°C to 8°C). The vials must be kept in the original package in order to protect from light. Vials should not be frozen. The unopened vial can be stored at controlled room temperature up to 25°C with room light for up to 48 hours.
- Infusion must be completed within 24 hours of preparation. If not used immediately, the solution may be stored under refrigeration conditions (2°C-8°C) and protected from light for up to 24 hours [a maximum of 8 hours of the total 24 hours can be at room temperature (20°C-25°C) and room light].
- Do not use after the expiry date which is stated on the carton and on the vial label after EXP. The expiry date refers to the last day of that month.
- Do not store any unused portion of the infusion solution for reuse. Any unused medicine or waste material should be disposed of in accordance with local requirements.

Preparation and administration of nivolumab;

- Visually inspect drug product solution for particulate matter and discolouration prior to administration. Nivolumab is a clear to opalescent, colourless to pale-yellow solution. Discard the vial if the solution is cloudy, discoloured, or contains extraneous particulate matter other than a few translucent-to-white, proteinaceous particles. Do

not shake the vial.

- Withdraw the required volume of nivolumab and transfer into an intravenous container. Dilute nivolumab with either 0.9% Sodium Chloride Injection, USP or 5% Dextrose/Glucose Injection, USP to prepare an infusion with a final concentration ranging from 1 mg/mL to 10 mg/mL. The total volume of infusion must not exceed 160 mL. For patients with body weights less than 40 kg, the total volume of infusion must not exceed 4 mL/kg of body weight.
- Mix diluted solution by gentle inversion. Do not shake
- The dose of nivolumab for administration must be prepared by the Investigator's or site's designated IP manager using aseptic technique. Total time from needle puncture of the vial to the end of administration should not exceed;
  - 8 hours at room temperature
  - 24 hours under refrigeration at 2°C to 8°C (36°F to 46°F)
- The infusion should be administered over 60 minutes through an intravenous line containing a sterile, non-pyrogenic, low protein binding in-line filter (pore size of 0.2 micrometre to 1.2 micrometre).
- Do not co-administer other drugs through the same intravenous line
- The intravenous line should be flushed at the end of the infusion.

### 6.2.3 Denosumab

Denosumab is a human monoclonal antibody (IgG2) that targets and binds with high affinity specifically to RANKL, preventing RANKL/RANK interaction from occurring and resulting in reduced osteoclast numbers and function, thereby decreasing bone resorption and cancer-induced bone destruction.

Denosumab is approved to be administered at 120 mg S.C. once monthly for use in the prevention of skeletal-related events in patients with advanced cancers with bone metastases (XGEVA®).

The use of denosumab in this trial is outside labelled use as patients may not have bone metastases. The rationale for its prophylactic use in all patients is as a bone protection measure based on the increased risk of bone fragility with RXC004 treatment.

## **6.3 Randomisation**

Once Arm B is opened, patients who are eligible for both Arm A and Arm B will be randomised 2:1 to Arm B: Arm A to ensure there is no conscious or unconscious selection bias. A 2:1 randomisation was selected to ensure that the combination and monotherapy arms will complete at approximately the same time and to maximise the number of patients recruited under randomisation conditions. Patients will be centrally assigned to a Study Arm using IRT.

Randomisation will be open-label, and will be stratified by genetic alteration (RNF43 vs RSPO).

## **6.4 Study Treatment Compliance**

### **6.4.1 RXC004**

The first dose of RXC004 will be taken at the site under medical supervision. The date and time of dose administered at site will be recorded in the source documents and recorded in the eCRF. When patients self-administer RXC004 at home, compliance with study treatment will be assessed at each visit. Compliance will be assessed by collection of a patient diary cards and counting of returned capsules, during the site visits and documented in the source documents and eCRF. Deviation(s) from the prescribed dosage regimen should be recorded in the eCRF.

A record of the number of RXC004 capsules dispensed to and taken by each participant must be maintained and reconciled with study treatment and compliance records. Treatment start and stop dates, including dates for treatment delays and/or dose reductions will also be recorded in the eCRF.

### **6.4.2 Nivolumab**

Nivolumab will be dosed at the site, directly from the investigator or designee, under medical supervision. The date, and time of dose administered at site will be recorded in the source documents and recorded in the eCRF. The dose of nivolumab and the study participant identification will be confirmed at the time of dosing by a member of the study site staff other than the person administering the study intervention.

## **6.5 Concomitant Therapy**

Any medication or vaccine (including over-the-counter or prescription medicines, vitamins, and/or herbal supplements) that the participant is receiving at the time of enrolment or receives during the study must be recorded along with:

- Reason for use
- Dates of administration including start and end dates

- Dosage information including dose and frequency

Concomitant medication may be given as medically indicated with the exception of prohibited concomitant medication (Section 5.3.3 and Appendix E). The Medical Monitor should be contacted if there are any questions regarding concomitant or prior therapy.

### **6.5.1 Rescue Medicine**

As a result of immune mediated AEs that could potentially be experienced by patients on nivolumab, steroids and other immunosuppressant rescue medication must be available to these patients. The two products that fall into the category of other immunosuppressants are infliximab (e.g., for colitis) and mycophenolate (e.g. for hepatitis). Rescue medications for immune mediated adverse events will be obtained locally.

The use of infliximab and mycophenolate are considered to be used as off-label for management of immunotherapy related toxicities. These rescue medications must be received, controlled, and administered by the pharmacist and stored according to the labelled storage conditions.

## **6.6 Dose Modification**

RXC004 dose reduction and interruption are permitted. Nivolumab dose reduction is not permitted but dose interruption/delay is permitted as per Appendix G.

RXC004 may be dose interrupted (withheld) until a clinically significant (any grade) and/or a grade  $\geq 3$  related adverse event resolves to baseline or  $\leq$  grade 2. RXC004 may also be withheld if it is necessary to give a concomitant medication that is a moderate or strong CYP3A4 inhibitor. RXC004 related colitis events should be managed as per Appendix J.

Adverse events that are assessed as being causally related nivolumab should be managed as per the Nivolumab Toxicity Management and Dose Modification Guidelines (Appendix G). If either agent is interrupted or discontinued for a related-AE the other agent (nivolumab or RXC004) may be continued if the patient is judged (by the investigator) to be receiving clinical benefit.

RXC004 and nivolumab dose interruption and stopping criteria are detailed in Table 14.

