## Assessment of potential for other risks

### Potential for Drug-Drug Interactions with CYP3A4 inhibitors

RXC004 has not shown the potential to induce or inhibit CYP enzymes or transporters at the dose to be investigated in this study but it is exclusively metabolised by CYP3A4 and as such has the potential to be a victim for drug-drug interactions with potent CYP inhibitors (which could increase levels of RXC004, leading to a higher risk of adverse events). As such, strong and moderate CYP3A4 inhibitors are contra indicated in this protocol (see Appendix E). Patients with colorectal cancers commonly require co-medication with analgesics, antibiotics, anti-emetics and anti-depressant or anxiolytic drugs, some of which are CYP3A4 inhibitors. The table in Appendix E highlights the CYP3A4 inhibitors which are also likely to be commonly used in colorectal cancer patients. These drugs should be avoided, and alternatives used wherever possible. If it is not possible to use an alternative (e.g. if a specific antibiotic or anti-fungal treatment is needed), RXC004 should be interrupted.

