#### **5.3.3 Concomitant treatments**

##### **5.3.3.1 Prohibited medications**

The following concomitant medication is prohibited without approval from the Sponsor Physician;

- 1 The use of any natural/herbal products or other 'folk remedies'.

- 2 No other chemotherapy, hormonal therapy (contraception and hormone replacement therapy is acceptable), or other investigational product is permitted other than the study treatments.
- 3 Live or live-attenuated virus and bacterial vaccines should not be administered, e.g. yellow fever, measles, influenza nasal spray, COVID-19, rubella, mumps, typhoid, mycobacterium tuberculosis (BCG), Yersinia pestis (EV) within 4 weeks of starting study treatment, whilst the patient is receiving study medication and for 30 days following discontinuation of study treatment. Patients who require COVID-19 vaccination whilst on study should receive a non-live vaccine (e.g. one based on mRNA or fully inactivated/genetically modified viruses incapable of replication).
- 4 The use of some CYP3A4 inhibitors and inducers should be restricted prior to first dose of study treatment and throughout the study treatment, as RXC004 is observed to be exclusively metabolised by CYP3A4. For a list of prohibited CYP3A4 inhibitors and inducers and the required washout periods, please refer to Appendix E.
- 5 Drugs that are immunosuppressive or may cause secondary osteoporosis should not be administered (e.g. corticosteroids, pioglitazone or rosiglitazone).

The following exceptions are allowed:

- Use of immunosuppressive medication for the management of nivolumab-related AEs (as per Appendix G) or colitis events (as per Appendix J). Steroids required for the management of RXC004 or nivolumab related AEs, should be tapered to doses  $\leq$  10 mg/day prednisone equivalent, before re-starting study treatment.
- Use of topical, inhaled or intranasal corticosteroids
- Systemic steroids at doses  $\leq$  10 mg/day prednisone equivalent

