Any event that meets nivolumab treatment hold (see Appendix G)	Interrupt nivolumab and manage as per Appendix G. Nivolumab can be re-started when event is resolved to ≤Grade 1 and any steroid taper completed (to ≤10 mg prednisone equivalent). RXC004 can continue whilst nivolumab is held if the patient is judged (by the investigator) to be receiving clinical benefit.
Grade 3 toxicity (1 st event)	RXC004 related; Interrupt RXC004 and provide supportive care, resume at a lower dose level when resolved (grade ≤ 2 or returns to baseline). See Table 15 for dose reduction scheme.
	Nivolumab related; See guidelines in Appendix G.
Grade 3 toxicity (subsequent recurrence of a previously experienced event)	RXC004 and/or nivolumab related; Permanently discontinue the related study treatment.

Event	Action
Grade 4 toxicity	RXC004 and/or nivolumab related; Permanently discontinue RXC004 and nivolumab (if applicable)
All Grade events	Study treatment can be interrupted or discontinued for any clinically significant AEs that in the investigator's opinion warrants treatment interrupted or discontinuation.
Bone events	
Confirmed (by imaging) RXC004 related fragility bone fracture (excluding grade 1 vertebral deformities)	Permanently discontinue RXC004. Nivolumab can continue if the patient is receiving clinical benefit as judged by the investigator.
Patients with a DXA scan showing $\geq 7\%$ worsening in BMD at lumbar spine or total hip compared to baseline	Permanently discontinue RXC004. Nivolumab can continue if the patient is receiving clinical benefit as judged by the investigator.
An individual increase in $\beta$ -CTX of CCI pg/ml from the baseline (screening) value or an individual measurement of CCI pg/ml	Permanently discontinue study treatment unless the patient has received clinical benefit (investigator assessment) and continued treatment is warranted.
COVID-19 infection	
Positive COVID-19 test	Interrupt RXC004, until acute symptoms have resolved.
Major surgery	
	Interrupt RXC004, resume at full dose. Nivolumab does not need to be interrupted.
	No stoppage is required for biopsy procedures.
Vomiting	
	If vomiting occurs shortly after RXC004 is swallowed, the dose may be replaced if all of the intact capsules can be counted. Resume with the following scheduled dose.
Missed RXC004 dose	

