## Appendix E Prohibited CYP3A4 Inhibitors, and Inducers

CYP3A4 Inhibitors	CYP3A4 Inducers

CYP3A4 Inhibitors
 
[Bold text denotes commonly used co-medications in patients with colorectal cancer]
	
CYP3A4 Inducers
 
[None of these drugs are commonly used co-medications in patients with colorectal cancer]

Strong CYP3A4 Inhibitors
 
Concomitant use of these drugs has the potential to increase the exposure of RXC004 over 5-fold
 
These agents must not be given within 14 days of first dose of study treatment
 
boceprevir, cobicistat, danoprevir and ritonavir, elvitegravir and ritonavir, grapefruit juice, indinavir and ritonavir, itraconazole, ketoconazole, lopinavir and ritonavir, paritaprevir and ritonavir and (ombitasvir and/or dasabuvir), posaconazole, ritonavir, saquinavir and ritonavir, telaprevir, tipranavir and ritonavir, troleandomycin, voriconazole, clarithromycin, idelalisib, nefazodone, neflifinavir,
	
Strong CYP3A4 Inducers
 
Concomitant use of these drugs has the potential to decrease the exposure of RXC004 by over 80%
 
aptalutamide, carbamazepine, enzalutamide, mitotane, phenytoin, rifampin, St. John's wort
 
These agents must not be given within 14 days of first dose of study treatment

Moderate CYP3A4 Inhibitors
 
Concomitant use of these drugs has the potential to increase the exposure of RXC004 by 2-5-fold
 
A washout period of 14 days is recommended and a minimum washout period of 5 half-lives (See SPC or USPI) is required before first dose of study treatment.
 
aprepitant, ciprofloxacin, conivaptan, crizotinib, cyclosporine, diltiazem, dronedarone, erythromycin, fluconazole, fluvoxamine, imatinib, tofisopam, verapamil lansoprazole
	
Moderate CYP3A4 Inducers
 
Concomitant use of these drugs has the potential to decrease the exposure of RXC004 by 60-80%
 
A washout period of 14 days is recommended and a minimum washout period of 5 half-lives (See SPC or USPI) is required before first dose of study treatment
 
bosentan, efavirenz, etravirine, phenobarbital, primidone

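### When a strong or moderate CYP3A4 inhibitor is unavoidable, Protocol 6.6 and 5.3.3.1 lack the firm RXC004 hold given in 2.3.1.2, and restart timing is not stated

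*Protocol*

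**What the plan says.** Five parts of the Protocol bear on this.

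- **Section 2.3.1.2** (drug-drug interaction risk) states that "strong and moderate CYP3A4 inhibitors are contra indicated in this protocol". It goes on to cover the patient for whom no substitute exists: "if a specific antibiotic or anti-fungal treatment is needed), RXC004 should be interrupted".
- **Section 6.6** (dose modification) treats the same situation as permissive: "RXC004 may also be withheld if it is necessary to give a concomitant medication that is a moderate or strong CYP3A4 inhibitor". It then refers the site onward: "RXC004 and nivolumab dose interruption and stopping criteria are detailed in Table 14".
- **Table 14** has rows for colitis, dysgeusia, other adverse events, bone events, COVID-19 infection, major surgery, vomiting and missed doses. It has none for a required CYP3A4 inhibitor.
- **Section 5.3.3.1** opens its list with "The following concomitant medication is prohibited without approval from the Sponsor Physician". The CYP3A4 item in that list reads "The use of some CYP3A4 inhibitors and inducers should be restricted prior to first dose of study treatment and throughout the study treatment" and refers to Appendix E. No hold of RXC004 is attached to an approval.
- **Appendix E** gives the potential effect on exposure: over 5-fold for strong inhibitors and, for moderate ones, "Concomitant use of these drugs has the potential to increase the exposure of RXC004 by 2-5-fold". Its washouts differ by class and all relate to the first dose of study treatment. Strong inhibitors are barred for 14 days beforehand. Moderate ones need at least 5 half-lives, with 14 days recommended.

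**The concern.** The firm rule sits in the risk background and the weaker one sits in the operative dosing section. A site or Sponsor Physician dealing with an unavoidable antifungal or antibiotic would look at 6.6, Table 14 and 5.3.3.1. None of these says that RXC004 must stop while the inhibitor is given.

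The case is foreseeable. Section 2.3.1.2 notes that these patients often need antibiotics, anti-emetics and other drugs that include CYP3A4 inhibitors. Appendix J suggests considering antifungal cover during the steroid taper for Grade 3 colitis, and it allows monotherapy patients to restart RXC004 afterwards without asking whether an inhibiting antifungal has cleared.

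What is at stake is exposure. RXC004 is cleared only through CYP3A4, and 3 mg QD was declared non-tolerated. Section 4.4.1.2 also shows how narrow the sponsor judged the margin to be. Dose escalation in combination stopped at 1.5 mg because 2 mg was expected to give slightly higher exposure, and possibly more adverse events, than 2 mg alone.

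**Working it through.** The plan states no figure to reproduce. The check is mainly a comparison of texts, followed by arithmetic for scale.

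**1. Does *may* in 6.6 simply list a permitted reason to hold?** Section 6.6 uses the same *may* for Grade 3 or higher related events. For a first Grade 3 event, Table 14 turns it into an instruction: "Interrupt RXC004 and provide supportive care, resume at a lower dose level when resolved". The CYP3A4 case gets no such firming up in Table 14. The table is not confined to toxicity, since COVID-19 and surgery have interruption rows, so leaving this case out is not a matter of scope.

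**2. Who can give the inhibitor?** Section 5.3.3.1 prohibits it without approval. Section 6.5 excludes prohibited drugs from permitted concomitant medication and sends questions to the Medical Monitor. What remains uncovered is approved use during treatment.

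**3. Is there a restart rule?** Table 15 footnote b lets RXC004 resume after an interruption if no other discontinuation criterion is met. It gives no timing relative to the inhibitor, and the Appendix E washouts apply only before the first dose.

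**4. Scale of exposure.** Inputs are the planned doses (2 mg monotherapy, 1.5 mg combination), the Appendix E fold values, and the Table 12 geometric mean AUC0-24 in h*ng/mL: 931 at 2 mg (N=4) and 706 at 1.5 mg with nivolumab (N=5).

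Equivalent dose = dose × fold, assuming dose-proportional exposure:
- moderate, monotherapy: 2 × 2 = 4 mg to 2 × 5 = 10 mg
- moderate, combination: 1.5 × 2 = 3 mg to 1.5 × 5 = 7.5 mg
- strong: over 10 mg and over 7.5 mg respectively

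AUC with a moderate inhibitor = AUC × fold:
- monotherapy: 931 × 2 = 1862 to 931 × 5 = 4655
- combination: 706 × 2 = 1412 to 706 × 5 = 3530

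A dose-proportional 3 mg value would be 931 × 1.5 = 1396.5. The low ends are 1862 / 1396.5 = 1.33 and 1412 / 1396.5 = 1.01 times that. The actual 3 mg AUC is redacted, and Section 4.4.1.3 says it rose by more than the dose did, so these ratios overstate the position of the low ends relative to real 3 mg exposure.

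**5. Time off drug if the hold is firm.** The reference period is 16 × 7 = 112 days to the week-16 DCR assessment.
- Course of the inhibitor, assumed 5-14 days (not in the documents): 5/112 = 4.5% to 14/112 = 12.5%.
- Washout after a strong inhibitor, 14 days: 14/112 = 12.5%. Course plus washout is 19-28 days, or 17.0-25.0%.
- Washout after a moderate inhibitor at the 5 half-life minimum, with half-life assumed to be 6-48 h (not in the documents): 1.25-10 days, or 1.1-8.9%. Course plus washout is 6.25-24 days, or 5.6-21.4%. If the recommended 14 days is used, the strong-inhibitor figures apply.

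**The case against.** The strongest reply is that the sponsor's choice is already on the page. Section 2.3.1.2 says to interrupt, Section 5.3.3.1 prohibits unapproved use, and Section 6.5 repeats the exclusion immediately before 6.6. A *may* in a list of permitted reasons does not override a directive elsewhere. On this view only a wording alignment is left. Much of that stands, and it rules out four stronger readings that a reader might infer:

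- **That the sections contradict each other outright.** They do not. Holding RXC004 satisfies both, and the difference is one of strength.
- **That a site may keep dosing with an inhibitor on its own authority.** Sections 5.3.3.1 and 6.5 prevent this. The gap opens only once approval is given.
- **That there is no restart rule at all.** Table 15 footnote b is a general one. What is missing is timing relative to the inhibitor.
- **That co-administration would take patients to non-tolerated exposure.** Appendix E calls its values potential. The Table 12 means rest on 4 and 5 patients, with CVs of 61.1% and 40.1%. The 10 mg experience is one patient. Tolerability was judged under continuous dosing, whereas an antibiotic course is short, and both Grade 2 colitis events at 3 mg appeared in Cycle 2.

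The reply does not remove the approved-use case. The three places that a site or Sponsor Physician would consult for it carry no hold, and the one that does is background text.

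**Conclusion.** The point holds as a difference in strength of instruction that leaves approved on-treatment use without a firm hold where it is needed, and without inhibitor-specific restart timing. It should be corrected because the correction is nearly free and bears on safety. It does not threaten the design.

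The potential size is a 2-fold to more than 5-fold rise in exposure if RXC004 continues. The upper part of that range lies well above a dose-proportional 3 mg. The lower part cannot be shown to reach the exposure that was not tolerated. This rests on the Appendix E fold values and on dose-proportional scaling. The documents give no frequency of co-administration, so the number of patients affected is unknown.

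**What to change.** 1. In Section 6.6, replace *may also be withheld* with *should be withheld*. This restates the rule in Section 2.3.1.2.
2. In Section 5.3.3.1, state that approval of a strong or moderate CYP3A4 inhibitor requires RXC004 to be held.
3. Add a Table 14 row: *Strong or moderate CYP3A4 inhibitor required: interrupt RXC004; resume after the inhibitor is stopped, timing agreed with the Sponsor Physician, using the Appendix E washouts by class as the default (strong: 14 days; moderate: at least 5 half-lives, 14 days recommended).*

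The restart default is new for on-treatment use. It is therefore offered as a default with discretion, and it keeps the two classes separate so that strong inhibitors do not inherit the shorter moderate minimum.

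The drafting cost is one word, one sentence, one table row and a site clarification letter. The clinical cost is time off RXC004. The hold during the inhibitor course already follows from Section 2.3.1.2, so only the washout is added.

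Under Table 15 footnote b, a patient who progresses while held loses the option of treatment beyond progression. With 20 evaluable patients in Arm A, any one patient whose disease-control status changed would move DCR by 1/20 = 5 percentage points.

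Some moderate inhibitors in Appendix E, such as diltiazem, verapamil and lansoprazole, may be needed long term. A patient who develops such a need on treatment and has no alternative would in effect stop RXC004, which Section 2.3.1.2 already implies.
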